10.3.2 Emergency Unmasking

Emergency unmasking should only be performed when necessary to treat the subject. Most often, knowledge of the possible treatment assignments is sufficient to treat a clinical trial subject who presents with an emergency condition.

The investigator should make every effort to contact the Medical Monitor to discuss the subject's emergency and the need to unmask prior to unmasking any subject.

In situations in which the investigator has tried but is unable to reach the Medical Monitor, best judgement on the part of the investigator should be used, based on the nature and urgency of the clinical situation, and may proceed with unmasking without having successfully reached and discussed the situation with the Medical Monitor. Once a subject's treatment assignment has been unmasked, the Medical Monitor should be notified within 24 hours of the unmasking of the treatment, without revealing the treatment.

As this is a fixed sequence clinical trial, every attempt will be made to maintain the masking for the other subjects in the event of an unmasking must occur, an unmasking procedure will be developed.

The emergency unmasking should be performed by the designated site personnel. The investigator must also indicate in source documents and the Case Report Form (CRF) that the mask was broken and provide the date, time, and reason for breaking the mask.

Any AE or Serious Adverse Event (SAE) associated with breaking the mask must be recorded and reported as specified in the protocol. The investigator has the responsibility to contact the

Sponsor (PI) in the event of a drug-related, serious, unexpected AE, the ProPharma Group or designee will be provided with the treatment assignment for the subject for regulatory reporting.

If treatment assignment is unmasked, the treatment will be discontinued immediately, and the subject will be discontinued from the clinical trial.

The mask may be broken in the case of pregnancy should the subject desire this information.

11. STUDY VISITS

11.1 COVID-19 Screening

The following procedures will be performed as part of COVID-19 screening:

- Subjects will be pre-screened based upon a COVID-19 questionnaire at each clinic visit.
- Body temperature will be measured at each visit.
- A nasal swab will be collected for COVID-19 testing on the day of Visits 1, 2 and 3.

Subject's further participation in the study will be based on the COVID-19 test results and procedures.

11.2 Visit 1: Screening (Day -21 to -8)

The following activities will be completed at Visit 1:

- Subjects will be asked to sign and date the Informed Consent Form.
- Demographic data, including date of birth, age, race and ethnicity, will be recorded.
- Medical/Medication and Ocular history will be completed for each subject.
- A urine pregnancy test will be performed (for all female subjects). Subjects with a positive result will be excluded.
- The subjects will be evaluated for study inclusion, exclusion and restriction criteria.
- Symptom Questionnaires (Ocular Discomfort Score, Ocular Itching Score) will be performed within 15 minutes prior to DEC entry and every 5 +2 minutes up to 45 minutes while in the chamber.
- An SVA and SLE will be performed pre and post-DEC.
- IOP will be performed prior to DEC entry and dilated funduscopy will be performed post-DEC.
- Saline will be administered in the clinic approximately 5 minutes prior to the DEC entry.
- DEC session (approximately 45 minutes).
- Adverse events and concomitant medications will be recorded before the subject leaves the site.
- After 7 ± 1 day of washout period, eligible subjects will come to Visit 2

11.3 Visits 2 (Day 1 + 2) and 3 (Day 8 + 2): Treatment/Dry Eye Chamber

Eligible subjects will return for 2 treatment visits. The treatment visits will occur following at least 7 days after visits 1 and 2. At Visit 2 the subjects will be randomized to receive one of the 2 treatment sequences as mentioned in [Section 10.2](#). At Visits 2 and 3, the following activities will be performed:

- Medical/medication and ocular history will be updated for each subject.
- A urine pregnancy test will be performed (for all female subjects). Subjects with a positive result will be excluded.
- The subjects will be evaluated for study inclusion, exclusion and restriction criteria.
- An SVA and SLE will be performed pre and post-DEC.
- Symptom questionnaires (Ocular Discomfort Score, Ocular Itching Score) will be performed within 15 minutes prior to study treatment administration and approximately every 5 minutes while in the chamber.
- Test product will be administered in the clinic approximately 5 minutes prior to the DEC entry.
- DEC session (approximately 45 minutes).
- Dilated funduscopy will be performed post-DEC after SVA and SLE at Visit 3.
- Adverse events and concomitants medications will be recorded before the subject leaves the site.
- Study exit (Visit 3).

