4. STUDY SUMMARY

Study Title	An Exploratory, Single-Center, Double-Masked, Crossover Clinical Trial to Assess Safety and Tolerability of 0.25% Reproxalap Ophthalmic Solution Compared to Xiidra® in Subjects with Dry Eye Disease in a Dry Eye Chamber
Protocol Number	C1D01056
Study Phase	Phase 2
Study Objectives	To explore the safety and tolerability of reproxalap compared to Xiidra® in a dry eye chamber.
Study Endpoints	
Exploratory Endpoints:
 
 • Change in ocular discomfort score (0-10) from baseline over 45 minutes in the dry eye chamber • Change in ocular itching score (0-10) from baseline over 45 minutes in the dry eye chamber 
Safety Endpoints:
 
 • Snellen visual acuity (SVA) • Slit-lamp examination (SLE) • Adverse event (AE) query
Study Design	C1D01056 is an exploratory, single-center, double-masked, crossover design trial to assess the safety and tolerability of reproxalap compared to Xiidra® in subjects with Dry Eye Disease (DED). The clinical trial will consist of 3 visits to the clinic over a period of approximately 34 days. This study will be an investigator-initiated trial.
Study Products and Treatment	
Treatment Products
 
Product A: 0.25% Reproxalap Ophthalmic Solution (reproxalap) (Manufactured by Aldeyra Therapeutics, Inc.)
 
Product B: Xiidra® (5% lifitegrast ophthalmic solution) [REDACTED]
 
Treatment products (reproxalap or Xiidra®) will be dosed topically in both eyes and administered once (1 drop in each eye) approximately 5 minutes prior to dry eye chamber (DEC) entry.

Route of Administration	Ophthalmic (topical ocular administration of eye drops)
Study Population	Approximately 50 subjects with DED, ages 18 to 70 years, are expected to be enrolled in the trial. The study will consist of 1 treatment group.
Study Conduct	The clinical trial will consist of 3 visits. At each visit, staff will update the subjects' concomitant medication and collect AEs. A urine pregnancy test will be administered to all female subjects. Coronavirus Disease 2019 (COVID-19) screening questionnaire, oral temperature and COVID-19 rapid test will be performed at Visits 1, 2 and 3. Eligibility

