	
criteria will be reviewed. There will be at least 7 days of washout period following Visits 1 and 2.
 
I. Medical Screening- Visit 1 (Day -21 to -8)
 
All subjects will undergo a medical screening visit (Visit 1), including written informed consent, demographics, medical/medication and ocular history. Intraocular Pressure (IOP) will be performed prior to DEC entry. SVA and SLE will be performed prior to DEC entry. Symptom questionnaires (Ocular Discomfort Score, Ocular Itching Score) will be performed approximately 15 minutes pre-saline dose and approximately every 5 (+2) minutes while in the DEC. Saline will be administered in the clinic approximately 5 minutes prior to DEC entry. Following DEC exit (approximately 45 minutes), SVA (EDTRS), and SLE will be performed following chamber exit. Dilated fundoscopy will be performed post-DEC after SVA and SLE. After at least 7 days of washout, subjects will return for Visit 2.
 
II. Treatment- Visit 2 (Day 1 + 2) and Visit 3 (Day 8 + 2)
 
A fixed treatment sequence is allotted for Visit 2 and 3. SVA and SLE will be performed prior to symptom questionnaires, and eligibility criteria will be reviewed. Symptom questionnaires (Ocular Discomfort Score and Ocular Itching Score) will be performed approximately 15 minutes pre-dose and approximately every 5 (+2) minutes while in the DEC. Test product will be administered in the clinic approximately 5 minutes prior to chamber entry. Subjects will be exposed to a DEC (approximately 45 minutes) with Ocular Discomfort Score and Ocular Itching Score assessments every 5 (+2) minutes. SVA (EDTRS) and SLE will also be performed following DEC exit. There will be at least 7 days of washout after Visits 1 and 2. Dilated fundoscopy will be performed post-DEC after SVA and SLE at Visit 3.

Inclusion Criteria
	
 1. Eighteen (18) to 70 years of age at the time of screening (either gender and any race). 2. Ability to provide written informed consent. 3. Reported history of dry eye for at least 6 months prior to Visit 1. 4. Reported history of the use of eye drops within 6 months but not within 2 weeks of Visit 1. 5. [REDACTED]

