5. STUDY SCHEMATIC

Table 5.1-1: Schedule of Assessments

Procedure	Visit 1 Day -21 to -8 Screening/Baseline	Visit 2 Day 1 + 2 Randomization/ Dry Eye Chamber	Visit 3 Day 8 + 2 Dry Eye Chamber
COVID-19 screening questionnaire, oral temperature and COVID-19 rapid test	X	X	X
Informed Consent	X		
Demographics	X		
Medical/Medication & Ocular History	X		
Medical/Medication Update		X	X
Urine Pregnancy Test (for all female subjects)	X	X	X
Dry Eye Chamber ¹	X	X	X
Symptom Questionnaires (Ocular Discomfort Score/Ocular Itching Score) ²	X	X	X
Inclusion/Exclusion Criteria Review	X	X	X
Snellen Visual Acuity ³	X	X	X
Slit-lamp Examination ³	X	X	X
Saline Instillation	X		
Intraocular Pressure (IOP)	X ⁴		
Dilated Fundoscopy	X ⁵		X ⁵
Randomization		X	
Test Article Instillation		X	X
Adverse Event /Concomitant Medication Query	X	X	X
Study Exit			X

¹Dry eye chamber exposure (approximately 45 minutes).

²Will be performed within approximately 15 minutes prior to the entry and every 5+2 minutes while in the chamber.

³Will be performed pre-chamber (prior to symptom questionnaires) and post-dry eye chamber.

⁴Will be performed prior to dry eye chamber entry. These tests will be performed prior to symptom questionnaires.

⁵Will be performed post-DEC after SVA and SLE

Note:

- 1. A washout period of at least 7 days following visits 1 and 2 is given in this study.
- 2. [REDACTED] training will be provided to the study participants at Visit 1, 2 and 3.

Table 5.1-2: Schedule of Subject Assessed Ocular Discomfort/Ocular Itching

Time points in minutes	0	5	10	15	20	25	30	35	40	45
Window (minutes)	-15	+2								
Visit 1, 2 and 3	X	X	X	X	X	X	X	X	X	X

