8. STUDY DESIGN

8.1 Overall Study Design

C1D01056 is an exploratory, single-center, double-masked, crossover design trial to assess the safety and tolerability of 0.25% Reproxalap Ophthalmic Solution (reproxalap) compared to Xiidra® (5% lifitegrast ophthalmic solution) in subjects with DED.

[REDACTED]

[REDACTED] The DEC can exacerbate the signs and symptoms of dry eye in

subjects with dry eye. The controlled environment, over time, allows evaluation of subject responses at any time point throughout the chamber session.

Subjects will be administered with the following:

Product A: 0.25% Reproxalap Ophthalmic Solution (reproxalap) administered 1 drop in each eye approximately 5 minutes prior to DEC entry.

Product B: Xiidra® (5% lifitegrast ophthalmic solution) administered 1 drop in each eye approximately 5 minutes prior to DEC entry.

This study will include 3 clinic visits over a period of approximately 34 days.

At Visit 1 Screening (Days -21 to -8), subjects who meet screening inclusion/exclusion criteria will be treated with 1 drop of saline in each eye. At Visit 2, (Day 1), subjects who continue to meet inclusion/exclusion criteria will be eligible to receive test products as described above.

At Visits 1, 2 and 3, assessments of ophthalmic evaluations will be collected [REDACTED]. In the event of an [REDACTED] failure, paper diary cards will be used as a backup to collect symptom scores. Ocular Discomfort Score (0 – 10) and Ocular Itching Score (0 to 10) will be employed for subject-reported symptoms of ocular discomfort and ocular itching, respectively. For each scale, 0 is no symptomatology and 10 is maximum symptomatology.

Ocular activity will be assessed by symptom questionnaires (Ocular Discomfort Score/Ocular Itching Score). Safety will be assessed before and after chamber exposure by SVA testing and SLE.

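### Does the 7 ± 1 day interval before Visit 2 in Section 11.2 conflict with the 7-day minimum stated elsewhere in a way that matters?

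*Combined protocol and SAP*

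**What the plan says.** The protocol describes the interval from Visit 1 to Visit 2 in several places.

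- Section 11.2, last bullet: "After 7 ± 1 day of washout period, eligible subjects will come to Visit 2".
- Section 11.3: "The treatment visits will occur following at least 7 days after visits 1 and 2".
- Section 4 (Study Summary), Visit 1 paragraph: "After at least 7 days of washout, subjects will return for Visit 2".
- Section 5, Note 1 under Table 5.1-1: "A washout period of at least 7 days following visits 1 and 2 is given in this study".

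The day windows are the same in the Study Summary, Table 5.1-1 and the headings of Sections 11.2 and 11.3: Visit 1 on Day -21 to -8, Visit 2 on Day 1 + 2 and Visit 3 on Day 8 + 2. Section 8.1 gives the overall length: "This study will include 3 clinic visits over a period of approximately 34 days". Saline is instilled at Visit 1, and the two study products are given at Visits 2 and 3.

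**The concern.** Seven minus one is six, so one sentence permits a gap that the other three statements forbid, and Section 11.3 follows only a few lines later. The upper end looks odd as well. As a two-sided window, 7 ± 1 stops at 8 days, yet the heading of the same section lets Visit 1 fall as early as Day -21.

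If both problems were real in practice, whether a given Visit 2 date was a protocol deviation would depend on which sentence the site or monitor read. In a crossover trial, any loose statement about washout also raises the question of carryover, which could distort the comparison of the two products.

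**Working it through.** **Inputs.** Visit 1 falls on one of 14 days (Day -21 to -8) and Visit 2 on one of 3 (Day 1, 2 or 3), which gives 14 × 3 = 42 pairs. The protocol does not say whether there is a Day 0, so both conventions are computed. It also does not say whether washout is counted as elapsed days or as full days between visits, so both are shown.

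**The plan's own figure first.** Counting both end days, Day -21 to Day 10 spans 31 days without a Day 0 and 32 with one. If Visit 2 is on Day 3 and Visit 3 follows 7 + 2 = 9 days later, on Day 12, the span is 33 or 34 days. The windows therefore reproduce the stated figure of approximately 34. A two-sided 7 ± 1 followed by 7 to 9 days would give at most 8 + 9 + 1 = 18. That gap comes from the same two-sided reading and is not a separate contradiction.

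**Elapsed interval under the windows.**

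- No Day 0: V2 − V1 − 1. Shortest: 1 + 8 − 1 = 8. Longest: 3 + 21 − 1 = 23.
- With Day 0: V2 − V1. Shortest: 1 + 8 = 9. Longest: 3 + 21 = 24.

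Full days between visits are one fewer: 7 to 22, or 8 to 23. On every convention, 0 of 42 pairs fall below 7.

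**Can a 6-day gap occur inside the windows?** With Visit 2 on Day 1, a 6-day elapsed gap puts Visit 1 on Day -6 (no Day 0) or Day -5 (with Day 0). A later Visit 2 moves it closer still to Day 1. Counted as 6 full days between visits (7 elapsed), Visit 1 falls on Day -7 or Day -6. All of these lie outside Day -21 to -8.

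**Upper end, if ± 1 is a two-sided window of 6 to 8 days.**

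| Counting | Pairs within 6 to 8 | Pairs above 8 |
|---|---|---|
| Elapsed, no Day 0 | 1 (Day -8 to Day 1) | 41 |
| Elapsed, Day 0 | 0 | 42 |
| Full days between, no Day 0 | 3 (Day -9 to 1, Day -8 to 1, Day -8 to 2) | 39 |
| Full days between, Day 0 | 1 (Day -8 to Day 1) | 41 |

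These are counts of permitted date pairs, not expected frequencies.

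**Upper end, if the sentence means that the washout must elapse before Visit 2.** There is then no cap, and 0 of 42 pairs conflict.

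**Washout between products.** This is the interval from Visit 2 to Visit 3. The Section 11.2 bullet does not mention it. Section 11.3 and Note 1 under Table 5.1-1 both set at least 7 days for it.

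**The case for a change.** The strongest case for acting is that visit timing has consequences here. Section 17.2.3 lists failure to attend visits on time as an example of non-compliance that can lead to early termination, Section 20.4 requires deviations to be documented and explained, and Section 19 has monitors check conduct against the approved protocol. Section 11.2 is also where staff would look when booking Visit 2. A Visit 1 on Day -15 followed by a Visit 2 on Day 1 meets the windows and the 7-day minimum (15 elapsed days, or 16 with a Day 0), yet would breach the bullet read two-sided. The interval also follows more than saline. Visit 1 includes a chamber session of about 45 minutes and dilated fundoscopy, and Section 8.1 says the chamber can worsen dry eye signs and symptoms.

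Part of this stands. The texts do disagree, no other passage resolves them, and a site booking from the bullet alone could schedule a 6-day gap. Such a date would, however, be out of window by the heading of the same section, so the looser sentence does not make it compliant. The deviation argument needs the two-sided reading, which the sentence does not force. The documents also show no residual chamber effect at 6 days.

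**Conclusion.** This is a clerical slip. The bullet in Section 11.2 is worded inconsistently with three other statements, and those passages must be reconciled; which interval to keep is for the sponsor. No change to the design, endpoints or analysis follows, and reconciling the wording would not alter any estimate, its bias or its precision.

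The lower end has no effect while the visit windows hold, because none of the 42 permitted pairs is shorter than 7 days on any counting convention. The upper end is a conflict only on the two-sided reading (39 to 42 of 42 pairs), and even then its effect is on the deviation log. The at-least-7-days sentences carry no cap of their own, but the windows limit the interval to 23 or 24 elapsed days.

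The conclusion rests on three points: sites schedule within the stated windows, Visit 1 gives saline only, and Section 14 names no analysis in which the Visit 1 to Visit 2 interval enters.

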6.4 Benefit/Risk Assessment

No clinically significant safety signals have been observed in more than 1200 subjects treated with topical ocular reproxalap. Generally, mild and transient instillation site discomfort is the most commonly reported adverse event. The acute tolerability of topical ocular reproxalap administration was characterized in two clinical trials where drop comfort was assessed and symptoms recorded within minutes of dosing. [REDACTED]

Similarly, ADX-102-AC-011 and ADX-102-AC-017 compared 0.25% reproxalap to the vehicle during peak symptomatology in an allergen chamber and indicated that reproxalap was statistically superior to the vehicle as soon as five to ten minutes after administration. [REDACTED]

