12.2.4 Dilated Fundoscopy

Examining the fundus is an effective strategy to acquire a sense of the subject total vasculature. The investigator or qualified staff will perform a dilated fundoscopy to evaluate clinically significant fundus abnormalities and vitreous pathology. Dilated fundoscopy will be performed at Visit 1 and 3 as per the site's Standard Operating Procedure.

Safety measurements may be obtained at the discretion of the Investigator in addition to the safety assessments described in this section.

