12.2.7 Adverse Event Query/Concomitant Medication Query

The staff will record all adverse events observed, queried, or spontaneously volunteered by the subjects. An adverse event query will be performed as scheduled as per Investigator's direction throughout the post-dose confinement period, prior to being released from confinement, and at each return visit for the study (if applicable). Subjects will be asked non-leading questions such

as “How do you feel now?”, “How have you felt since last asked?” or “Have you taken any medication since last asked?” If the presence of any symptom(s), adverse event(s), and/or concomitant medication is recorded, the clinical staff may advise the subjects to remain at the clinic site for safety reasons until the Investigator decides it is safe for the subjects to leave. If the subject decides to leave despite the Investigator's advice, he/she will be asked to sign a waiver.

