14.2 Safety Analysis

Safety analysis will include descriptive analysis and listings according to received treatment. Safety analysis will be performed on all subjects receiving at least one dose of study medication. Subject's safety data will be presented according to the treatment they actually received. The Safety population will be used for all analyses of safety endpoints as well as demographics and baseline characteristics.

Adverse events and SAE will be classified using standard Medical Dictionary for Regulatory Activities (MedDRA) terminology Version 23.1 and presented by the treatment group. Summary tables listing the type, date of onset, date and time of resolution, incidence, severity, outcome, action taken, and Investigator's opinion of relationship to the study product will be presented by treatment group for AEs reported after randomization.

Concomitant medication used during the study will be listed by treatment and subject.

14.3 Interim Analyses No interim analysis is planned at this point.

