17.2.1 Recording Adverse Events

The staff will record all AEs observed, queried, or spontaneously volunteered by the subjects (regardless of seriousness or relationship to study treatment) in the appropriate section of the subject’s case report form or source documents. Subjects experiencing AEs (including those withdrawn from the study due to an AE) will be followed until recovery to a satisfactory state, or stabilization, or appropriate outcome is established as judged by the Investigator. Exacerbation of conditions related to the signs and symptoms of Dry Eye will not be reported as an AE.

The following details will be recorded for AEs:

- Description of event/symptom
- Onset date and time of event
- End date and time of event
- Maximum severity/intensity rated as follows:
 - Mild: Causing no limitation of usual activities, the subject may experience slight discomfort.
 - Moderate: Causing some limitation of usual activities, the subject may experience annoying discomfort
 - Severe: Causing inability to carry out usual activities, the subject may experience intolerable discomfort or pain
- Action taken with study treatment noted as follows:
 - Dose not changed

- Dose reduced
 - Drug interrupted
 - Drug withdrawn
 - Not applicable
 - Unknown
- Any other action taken (such as concomitant medication, non-drug therapy, hospitalization or none)
- Outcome of AE noted as follows:
 - Fatal
 - Not recovered/not resolved
 - Recovered/resolved
 - Recovered/Resolved with sequelae
 - Unknown
- Causality noted as follows:

Related:	A causal relationship between the study treatment and the AE is a reasonable possibility.
Not Related:	A causal relationship between the study treatment and the AE is not a reasonable possibility.

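### Only one of the two treatment visits includes pupil dilation, and the by-treatment AE tables have no rule separating events that start after it

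*Combined protocol and SAP*

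**What the plan says.** **Where dilation occurs.** Section 12.2.4 states: "Dilated fundoscopy will be performed at Visit 1 and 3 as per the site's Standard Operating Procedure". Section 11.3 states for the treatment visits: "Dilated funduscopy will be performed post-DEC after SVA and SLE at Visit 3". The Section 4 summary and footnote 5 of Table 5.1-1 give the same position, after the chamber and after SVA and SLE. Visit 2 has no dilation. The Visit 1 dilation belongs to a saline session before randomization (Section 11.2: "Saline will be administered in the clinic approximately 5 minutes prior to the DEC entry").

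**When AEs are collected.** Section 11.3, for both treatment visits: "Adverse events and concomitants medications will be recorded before the subject leaves the site". Section 12.2.7 places the query, as the Investigator directs, "throughout the post-dose confinement period, prior to being released from confinement", and at any return visit.

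**What is recorded.** Section 17.2.1: "The staff will record all AEs observed, queried, or spontaneously volunteered by the subjects (regardless of seriousness or relationship to study treatment". Its one stated exclusion is worsening of dry eye signs and symptoms. The AE form takes onset date and time and a two-level causality judgement, related or not related to study treatment.

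**How AEs are tabulated.** Under Section 14.2, safety data follow the treatment actually received, and the AE summaries "will be presented by treatment group for AEs reported after randomization". The table contents include the Investigator's opinion of relationship and the date of onset, but not the time of onset.

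**The concern.** The AE query is one of three safety endpoints, and the only objective is comparative safety and tolerability. SVA and SLE are done before dilation, so dilation cannot affect them. No AE query is required at that same point. The release query at Visit 3 therefore covers a period that includes an extra eye procedure, and the release query at Visit 2 does not.

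Section 6.4 says of reproxalap that "mild and transient instillation site discomfort is the most commonly reported adverse event". An eye complaint that starts during or after dilation could be hard to tell from a product effect in a summary table that shows only the onset date. At stake is whether AE incidence by product reflects the product alone, or the product plus a procedure done at one treatment visit only.

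**Working it through.** The plan gives no figure to reproduce. The sample size of 50 (Section 9.1) has no error rate, power or effect size behind it, and the question is where events are counted.

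**Step 1: order of procedures.**

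| | Visit 2 | Visit 3 |
|---|---|---|
| Test product, about 5 minutes before the chamber | yes | yes |
| Chamber, about 45 minutes | yes | yes |
| SVA and SLE after the chamber | yes | yes |
| Dilated fundoscopy | no | yes |
| AE recording before leaving | yes | yes |

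The bullets in Section 11.3 are not in time order: the SVA and SLE bullet precedes instillation. The position of dilation therefore rests on Section 4 and footnote 5 of Table 5.1-1. The position of the last AE query rests on Section 12.2.7, which ties it to release.

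**Step 2: which events count.** A Visit 3 event with onset after dilation is recorded whatever its cause, unless it is dry eye exacerbation. It comes after randomization, so it enters the by-treatment tables. Section 14.2 gives no explicit rule for assigning an AE to a crossover period; the natural reading of treatment actually received is the product given that day. A Not Related judgement is displayed but does not remove the event from the incidence count.

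**Step 3: effect of the sequence.** Sections 4, 10.2 and 10.3.2 describe a fixed sequence. Section 11.3 has subjects randomized at Visit 2 to one of two sequences. Section 15.1 speaks of randomization into a fixed sequence.

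Let d be the share of subjects with a recordable AE caused by dilation. The documents give no value, so 2% to 20% is an assumption. All 50 subjects are assumed to complete Visit 3.

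- One order for all: expected dilation AEs = 50 × d on the Visit 3 product and 0 on the other. The chance of at least one is 1 − (1 − d)^50.
- Two orders split 25:25: expected dilation AEs = 25 × d on each product.
- Spurious difference under one order, with background AE rate b on both products and independence: [1 − (1 − b)(1 − d)] − b = (1 − b) × d. The values b = 5% and b = 15% are also assumptions.

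| d | One order: Visit 3 product vs other | Chance of at least one | Spurious difference, b = 5% | Spurious difference, b = 15% | Two orders: each product |
|---|---|---|---|---|---|
| 2% | 1.0 vs 0 | 0.64 | 1.9 points | 1.7 points | 0.5 |
| 5% | 2.5 vs 0 | 0.92 | 4.8 points | 4.3 points | 1.25 |
| 10% | 5.0 vs 0 | 0.995 | 9.5 points | 8.5 points | 2.5 |
| 20% | 10.0 vs 0 | >0.999 | 19.0 points | 17.0 points | 5.0 |

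Under two orders split 25:25, the expected difference between products is zero.

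**The case against.** The case against giving this much weight is substantial.

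- **No documented rate.** The protocol names no dilating agent and gives no symptoms or rate of dilation events. Staff might not record expected, passing effects of an examination as AEs. This stands: the table above shows scale only.
- **The dry eye exclusion.** Section 6.1 lists irritation, burning and ocular pain among dry eye symptoms, so Section 17.2.1 may already remove some complaints of this kind. This stands in part; the exclusion does not mention procedure-related events.
- **Earlier queries and onset time.** Section 12.2.7 allows queries during confinement, and onset time is on the AE form. Section 6.4 describes acute tolerability assessed within minutes of dosing, whereas dilation follows a chamber session of about 45 minutes. The data could therefore separate most events. This stands as to feasibility, but no query is required before dilation and Section 14.2 does not use onset time.
- **The sequence is the larger problem.** Under one fixed order, product is confounded with visit for every endpoint, and separating dilation events does not cure that. This stands.

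A reader might infer that the plan builds in a bias against one product, or that it attributes dilation effects causally to that product. The documents support neither. Bias between products arises only if every subject follows the same order. Counting an event under a product is not a causal judgement, and relationship is reported alongside. A reader might also infer added noise in a within-subject AE comparison, but Section 14.2 plans descriptive summaries and listings and no such comparison.

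**Conclusion.** The point holds as a gap in tabulation. Of the two treatment visits, only Visit 3 has dilation between the product and the release query, and nothing in Section 14.2 separates events that start afterwards. Under one fixed order, those events all fall on one product and confound procedure with product. Under two balanced orders, they add background about equally to both.

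The size is unknown. About 1 to 10 events in 50 subjects follows only from assumed rates of 2% to 20%, with everyone completing Visit 3 and none of the events excluded as dry eye exacerbation. The study is exploratory and descriptive, and onset time and relationship are already collected, so this is a minor point and a cheap improvement.

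**What to change.** 1. **Sequence text.** Reconcile Sections 4, 10.2, 10.3.2, 11.3 and 15.1, so that it is clear whether there is one order or two. This determines whether the point affects the comparison between products.
2. **Section 11.3.** Specify an AE query after the post-chamber SVA and SLE at both Visit 2 and Visit 3, placed before dilation at Visit 3. Keep the release query at both visits. Record the time of dilation. The dilation procedure and its place in the visit do not change.
3. **Section 14.2.** Keep the all-AE table by product. Add an on-site incidence table by product with the same cut-off at both visits, from dose to the post-SVA/SLE query, using the onset time collected under Section 17.2.1. Show Visit 3 events with onset after dilation in a separate row with their relationship. The common cut-off matters: truncating or adding a query at Visit 3 alone would create a new imbalance.

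The cost is one short query per treatment visit, one time field, a few sentences and one extra table. The downside is that a product effect starting after the cut-off is absent from the on-site table, though it stays in the all-AE table.
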